In less than five months since the emergence of a novel coronavirus (SARS-CoV-2) in December 2019, millions of patients worldwide have suffered acute respiratory conditions, many of whom ultimately require mechanical ventilation due to hypoxemic respiratory failure. This disease (COVID-19) has been associated with a hyperinflammatory and hypercoagulable state¹ leading to a range of thromboembolic complications from pulmonary embolism to ischemic stroke.^{2,3} Furthermore, emerging data suggest that the associated acute respiratory failure is, at least in part, due to pulmonary vascular disease caused by micro- and/or macro-emboli creating pulmonary vascular shunting and dead-space ventilation.^{4,5} The relatively preserved lung compliance, particularly in certain individuals and early in the disease course, has brought into question whether the respiratory failure is in fact caused by the traditional acute respiratory distress syndrome (ARDS).^{6,7}

Given these observations, in the early phase of the COVID-19 pandemic hitting New York City, critically ill patients with severe hypoxemic respiratory failure due to COVID-19 were treated with intravenous thrombolysis with alteplase, tissue plasminogen activator (tPA). In a case series of four patients, rapid physiologic improvements in alveolar ventilation, oxygenation, and/or hemodynamics was noted.¹⁸ Wang et al⁸ also noted similar results with tPA in this patient population. In both of these case series, the physiologic effects of tPA were only temporary. It was only with the concomitant use of anticoagulation with heparin were these physiologic benefits sustained, likely because anticoagulation prevented immediate rethrombosis in this exceptionally prothrombotic condition.¹⁸ Given that tPA is contraindicated for concomitant use with heparin infusion, this protocol is created to assess tenecteplase as a thrombolytic agent in patients with COVID-19, as there is a very long-standing literature documenting the safety of tenecteplase with concomitant heparin infusion. There is an additional logistic benefit to tenecteplase, in that it is given as a single bolus. The logistic challenges of providing a prolonged alteplase infusion to a COVID-19 patient, wherein the IV pumps are outside the room and the IV tubing is in excess of 7 feet long, is quite formidable.

1.2 **CURRENT THERAPIES AND UNMET MEDICAL NEED**

Currently, there is no proven therapy for COVID-19 associated respiratory failure. A recent publication has suggested that systemic anticoagulation may help these patients¹⁹, but the data is far from definitive. Additionally, a case series and ongoing clinical trial (at other centers) is assessing the potential value of tPA thrombolysis in this patient population. We believe that TNK is uniquely situated to be of benefit for this population.

1.3 **BACKGROUND ON TENECTEPLASE**

Tenecteplase (TNKase[→]) is a modified form of human tissue plasminogen activator (tPA) that binds to fibrin and converts plasminogen to plasmin. In vitro studies demonstrated that in the presence of fibrin, tenecteplase conversion of plasminogen to plasmin is increased relative to its conversion in the absence of fibrin. This fibrin specificity decreases systemic activation of plasminogen and the resulting degradation of circulating fibrinogen compared with a molecule lacking this property, which could potentially decrease the incidence of bleeding.

Tenecteplase–Icahn School of Medicine at Mount Sinai
Protocol ML42492

Refer to the Tenecteplase Investigator's Brochure for details on nonclinical and clinical studies.

1.3.1 Approved Indication in US and Europe

In the US, TNKase® (tenecteplase) is indicated for use in the reduction of mortality associated with AMI.

1.4 OVERVIEW OF CLINICAL DEVELOPMENT

Tenecteplase has been previously developed in other indications and has been approved for the treatment of AMI. Tenecteplase is being developed by Genentech as a treatment for AIS 4.5 to 24 hours after stroke onset, in patients who show a salvageable brain pattern by advanced imaging technology.

Tenecteplase has been studied extensively in patients with acute myocardial infarction (AMI). The ASSENT-2 trial,⁹ for example, analyzed 16,949 patients with AMI randomized to either IV bolus of tenecteplase or infusion of alteplase, followed by maintenance therapy with heparin for 48-72 hours (goal aPTT 50-75). All-cause mortality was nearly identical between the two groups; however, the authors noted a pragmatic advantage inherent with a single bolus of tenecteplase compared to an infusion of alteplase. Tenecteplase is also associated with a lower rate of systemic bleeding compared to alteplase. The ASSENT-3 and ASSENT-3 PLUS trials provide further confirmation of the safety of anticoagulation administration following tenecteplase.^{10,11}

Tenecteplase has been studied for patients with pulmonary embolism.¹⁵ In the PEITHO trial, the use of tenecteplase at a dose of 0.5 mg/kg with concomitant anticoagulation reduced the rate of hemodynamic decompensation in patients with intermediate-risk pulmonary embolism. This benefit, along with lower bleed rates, was particularly notable in participants younger than 75 years old. Eight of 13 (62%) participants who suffered stroke in PEITHO were > 75 years old; two of the eleven (18%) participants who suffered hemorrhagic stroke were < 75 years old. Completed and ongoing clinical studies of tenecteplase are summarized in the Tenecteplase Investigator's Brochure.

1.4.1 Acute Myocardial Infarction Clinical Development

Tenecteplase is indicated for use in the reduction of mortality associated with AMI and has been approved since 2000. Completed and ongoing clinical studies of tenecteplase are summarized in the Tenecteplase Investigator's Brochure.

1.4.2 Acute Ischemic Stroke Clinical Development

Tenecteplase is being evaluated for safety and efficacy in a Phase III in AIS stroke patients, 4.5–24 hours after symptom onset, who show a salvageable brain pattern by advanced imaging technology (Study ML40787). Study ML40787 TIMELESS (Thrombolysis in Imaging Eligible Late Window Patients to assess the efficacy and safety of Tenecteplase) is currently enrolling and plans to enroll 456 acute ischemic stroke patients in the US and Canada. Patients with large vessel occlusions, with a diffusion/perfusion mismatch, in the 4.5–24 hour window may be eligible to receive tenecteplase 0.25 mg/kg or placebo in conjunction with mechanical thrombectomy.

Tenecteplase–Icahn School of Medicine at Mount Sinai
Protocol ML42492

Completed and ongoing clinical studies of tenecteplase are summarized in the Tenecteplase Investigator's Brochure.

Studies have also demonstrated the benefit of tenecteplase in acute ischemic stroke. In the EXTEND-IA TNK trial,¹³ tenecteplase combined with endovascular thrombectomy was associated with higher probability of radiographic reperfusion as well as long term functional outcomes in patients with large vessel intracranial occlusions as compared to alteplase. This benefit was seen at a lower dose (0.25 mg/kg) than the MI studies (0.5 mg/kg). A subsequent study, EXTEND-IA TNK II, found no increased risk but no clinical benefit in stroke to increasing the TNK dose to 0.4 mg/kg.¹³ Further studies are in progress to assess a longer window to treatment time, including a Phase III clinical trial for patients with a salvageable penumbra on brain perfusion imaging.¹⁴

1.5 STUDY RATIONALE AND BENEFIT-RISK ASSESSMENT

Based on a recent JAMA publication, intubated COVID-19 patients in NYC can expect a mortality rate as high as 88%.¹⁶ This dismal mortality rate has driven us to make clinical decisions regarding the use of off-label application of otherwise FDA approved medications in a hope to improve outcomes. Therefore, we undertook the off-label utilization of tenecteplase (at the lower EXTEND-IA TNK dosing) with concomitant heparin administration for the treatment of 5 refractory COVID-19 patients. We were highly encouraged by this experience in that all patients had improvement in oxygenation, alveolar ventilation, and hemodynamics within 24-48 hours. Four of the five patients had shock resolution, while the fifth patient had dramatic reductions in vasopressor requirements. No clinically significant bleeding was noted in any of these patients. As a result, we believe that a high-quality prospective Phase II, dose escalation trial is indicated.

To assess the efficacy of tenecteplase on critically ill patients with COVID-19 and hypoxic respiratory failure, we propose a multi-center, randomized, controlled, double-blind, dose-escalation trial comparing tenecteplase versus placebo. We intend to enroll 60 subjects: 40 randomized for intervention (20 each at doses of TNK, 0.25 mg/kg and 0.50 mg/kg) and 20 for placebo. Planned inclusion criteria are confirmed respiratory failure requiring mechanical ventilation for not greater than 48 hours, or non-rebreather (NRB), high-flow nasal cannula (HFNC), or non-invasive positive pressure ventilation (NIPPV) for less than 96 hours, with confirmed infection with SARS-CoV-2 virus (PCR positive within 14 days), elevated D-dimer (2 times upper limit of normal,¹⁷ and lack of stringent exclusion criteria. Primary efficacy outcome will be clinical status assessment at 28 days (proportion of patients alive and free of respiratory failure). Primary safety outcome will be rate of ICH or major acute hemorrhage (defined as bleeding episode leading to hemodynamic compromise requiring emergency intervention [such as replacement of fluid and/or blood products, inotropic support, or surgical treatment], or life-threatening or fatal bleeding). Secondary outcomes include survival, ventilator-free days, respiratory failure-free days, vasopressor-free days, improvement in PaO₂/FiO₂, and ICU and hospital length of stay.

2. OBJECTIVES AND ENDPOINTS

2.1 PRIMARY OBJECTIVE(S)

The study objective is to evaluate the potential effect of tenecteplase on patients presenting with COVID-19. The hypothesis is that administration of the drug, in conjunction with heparin anticoagulation, will improve patients' clinical outcomes.

2.2 PRIMARY EFFICACY OUTCOME

The primary efficacy outcome will be the proportion of patients alive and free of respiratory failure (defined as not requiring non-rebreather, high-flow nasal cannula, non-invasive positive pressure ventilation, or mechanical ventilation) at 28 days.

2.3 STUDY OUTCOMES

The following outcomes will be tracked for the trial:

Primary outcome is: the proportion of patients alive and free of respiratory failure (not requiring non-rebreather, high-flow nasal cannula, non-invasive positive pressure ventilation, or mechanical ventilation) at 28 days

- A. Primary safety outcome: Occurrence of intracranial bleeding or major bleeding (Definition: A bleeding episode leading to hemodynamic compromise requiring emergency intervention (such as replacement of fluid and/or blood products, inotropic support, or surgical treatment), or life-threatening or fatal bleeding) within 72 hours of randomization. All outcomes will be assessed in a blinded fashion by the DSMC/CEC.
- B. Secondary outcomes include: 14-day in-hospital mortality, 28-day mortality, ventilator-free days, respiratory failure-free days (not requiring NRB, HFNC, NIPPV, or mechanical ventilation), vasopressor-free days, vasopressor requirements at 24 and 72 hours, P/F ratio at 24 hours and 72 hours, ICU-free days, hospital length of stay, new renal failure, need for renal replacement therapy
- C. Mortality: given a high mortality rate amongst this patient population, patients who die will be included in statistical analysis. Variables of interest will be calculated until the point these patients expire.

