3.2 END OF STUDY AND LENGTH OF STUDY

The anticipated first patient, first visit will occur on June 15, 2020. Enrollment is anticipated to take approximately 5 months, with our last patient, first visit to occur on November 15, 2020. Follow up will be completed by December 15, 2020. It will take the study team approximately 2 Tenecteplase-Icahn School of Medicine at Mount Sinai Protocol ML42492

months to clean and analyze the data, with a final study report expected by mid-February, 2021.

The total length of the study, from screening of the first patient to the end of the study, is expected to be approximately 8 months.

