4.5.6 End of Study (Day 28)

The following assessments will be collected at the final End of Study timepoint if the patient is still admitted:

- Neurological Exam

- Vitals

- Laboratory Samples (Standard of care)

Tenecteplase–Icahn School of Medicine at Mount Sinai
Protocol ML42492

20

Thromboelastograms (when available according to standard practice)

- Respiratory Status / Ventilator Settings
- Imaging (Standard of Care)
- Concomitant medication review (excluding “prn” or “as needed” medications)

The ordinal scale assessment will be completed at day 28 regardless of whether the patient is admitted or discharged.

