6. STATISTICAL CONSIDERATIONS

6.1 DETERMINATION OF SAMPLE SIZE

Assuming a total of 60 subjects enrolled with a 2:1 ratio in the tenecteplase:control arms and a good outcome rate of 15% in the control arm, this study has approximately 70% power to detect an absolute difference of 35% in the good outcome rate between the combined tenecteplase arms (40 patients) and the control arm (20 patients) and approximately 55% power to detect an absolute difference of 35% between each of the tenecteplase arms (20 patients) and the control arm (20 patients), at the 2-sided 0.05 significance level based on the Fisher's exact test. Good outcome rate is defined as the proportion of patients who are alive and free of respiratory failure at 28 days. If the true rate of symptomatic ICH or major bleeding requiring transfusion is 3%, the chance of observing at least one of these events in 20 patients is at least 45%. The chance of observing at least one event in 20 patients increases to at least 70% if the true event rate is 6%.

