6.5 METHOD OF ANALYSIS

Continuous and categorical variables will be presented and summarized by using means with standard deviations and frequencies with percentages respectively. Tukey's method for pairwise comparison and large sample based multiple comparison of logits will be performed for continuous variables. Logistic regression modeling will be used for covariates adjustments and subgroup analyses. Survival functions will be estimated by applying Kaplan-Meier method. Statistical testing will be performed at two-sided 5% level of significance.

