
Tenecteplase-Icahn School of Medicine at Mount Sinai
Protocol ML42492

45

Appendix 1

Study Flowchart

	Screening	Enrollment/Randomization ^a		Follow Up Period (Day 4 to 27 post randomization)	End of Study (Day 28 OR Discharge)
		Pre-Randomization (must be collected within 2 h of study drug administration)	Post Randomization q6 hr. to 72 hr.		
Informed Consent	x				
Demographics	x				
Medical History	x				
Inclusion/Exclusion Criteria	x	x			
Weight for Dosing	x				
Vital Signs ^b	x	x	x	x	x
PCR COVID Test	x				
Lab Testing ^c	x	x	x ^d	SOC	SOC
Arterial Blood Gas ^e	x	x	x [*]	SOC	
Respiratory Status/Ventilator Settings ^f	x	x	x	x ^{**}	x
Ordinal Scale	x	x	x	x	x
Neurological Exam ^g	x	x	x	x	x
Vasopressor Dosing	x	x	x	x	
TNK-tPA Dosing			x		
Heparin Dosing ^h	x***	x***	x	x	
Imaging ⁱ	SOC		SOC	SOC	SOC
Pregnancy Test ^j	x				
Adverse Events/ SAE Review ^k	x	x	x	x	x
Concomitant Medications	x	x	x	x	x

Tenecteplase–Icahn School of Medicine at Mount Sinai
Protocol ML42492

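### Hospital length of stay is to be averaged, but no discharge date after Day 28 is scheduled and no rule covers survivors still admitted, while deaths count as short stays

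*Combined protocol and SAP*

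**What the plan says.** Hospital length of stay appears twice as a secondary outcome. Section 2.3 has "ICU-free days, hospital length of stay, new renal failure, need for renal replacement therapy" and Section 1.5 has "ICU and hospital length of stay". Neither gives a time origin, a horizon, or a rule for a patient who has not left hospital when follow-up ends.

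Scheduled data stop at Day 28:
- Section 4.5.6 opens with "The following assessments will be collected at the final End of Study timepoint if the patient is still admitted", so the plan itself expects some patients to be inpatients then.
- The last column of the Appendix 1 flowchart is headed "End of Study (Day 28 OR Discharge", and nothing follows it.
- Section 3.2 expects the "last patient, first visit to occur on November 15, 2020" and states "Follow up will be completed by December 15, 2020", which is 30 days later.

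For analysis, Section 6.5 has continuous variables "summarized by using means with standard deviations" and compares them by Tukey's method. Kaplan-Meier is named for survival functions only and is not assigned to discharge. Last value carried forward appears only under the primary efficacy variable (6.2). Item C of Section 2.3 keeps patients who die in the analysis, with their variables computed up to death.

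**The concern.** A stay that is still running when observation ends is right-censored. An ordinary mean cannot use it: the analyst must either enter the days seen so far or leave the patient out. Both understate the mean, because these are the longest stays. The plan does not say which to do.

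Death pulls the same summary down for a different reason. A patient who dies early contributes few hospital days, so a high-mortality arm can look as if it uses less hospital care.

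The trial is meant to estimate a benefit signal for a later phase III study (Section 3.3). A secondary outcome whose arm difference can point the wrong way is of little use for that.

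**Working it through.** The documents give no figure for length of stay, so there is none to reproduce. The check asks how many stays would be censored and what the planned mean would then show.

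**Step 1. Censored stays among controls.** Section 6.1 assumes "a good outcome rate of 15% in the control arm". Of 20 controls, 0.85 x 20 = 17 are then dead or in respiratory failure at Day 28. Assume that patients alive on respiratory support are inpatients; the documents do not say so. The minimum number censored is 17 - 20 x mortality. It is a minimum because patients off support but still admitted would add to it.

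| Assumed 28-day control mortality | Minimum censored, of 20 |
|---|---|
| 40% | 17 - 8 = 9 |
| 50% | 17 - 10 = 7 |
| 60% | 17 - 12 = 5 |
| 70% | 17 - 14 = 3 |
| 80% | 17 - 16 = 1 |
| 85% or more | 0 |

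**Step 2. Inputs for an illustration.** From Section 6.1: good outcome 15% in controls, and 15% + 35% = 50% on tenecteplase. Assumed: mortality 50% v 30%; a stay of 20 days from randomization for recovered survivors; X = 10, 20 or 30 further days after Day 28 for those still on support; all deaths in hospital at day d = 5, 10 or 15. The share alive on support is 1 - 0.50 - 0.15 = 0.35 in controls and 1 - 0.30 - 0.50 = 0.20 on tenecteplase.

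**Step 3. All-patient mean with stays cut at Day 28 and deaths counted to death (2.3, item C).**
- Control: 0.15 x 20 + 0.35 x 28 + 0.50d = 12.8 + 0.50d
- Tenecteplase: 0.50 x 20 + 0.20 x 28 + 0.30d = 15.6 + 0.30d
- Control minus tenecteplase: -2.8 + 0.20d = -1.8, -0.8 or +0.2 days for d = 5, 10 or 15

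**Step 4. What the cut removes.** Uncut, the arms gain 0.35X and 0.20X, so the cut takes 0.15X = 1.5, 3.0 or 4.5 days off the arm difference. This does not depend on when deaths occur.

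**Step 5. Dropping the censored patients instead.** At d = 10 the means are (3 + 5)/0.65 = 12.3 days for control and (10 + 3)/0.80 = 16.3 days for tenecteplase, a difference of about -3.9 days.

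**Step 6. Later discharge dates alone.** The uncut difference is -2.8 + 0.20d + 0.15X. At d = 5 and X = 10 it is -2.8 + 1.0 + 1.5 = -0.3 days. Longer follow-up removes the censoring but not the effect of counting deaths as short stays.

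**Step 7. The proposed measures in the same example.** Discharged alive by Day 28: 15% v 50%. Hospital-free days to Day 28 with deaths set to 0: 0.15 x 8 = 1.2 v 0.50 x 8 = 4.0. Neither depends on d or X.

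**The case against.** The strongest reply is that little rests on this outcome. It is one of many secondary outcomes in a 60-patient trial that Section 3.3 says is not sized to show significance, and no stopping, escalation or primary decision uses it. That stands and sets the severity.

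The mortality range is also assumed. Section 1.5 cites mortality as high as 88%, and at 85% or more the guaranteed number of censored controls is zero. That figure is an upper value for intubated patients, while Section 4.1.1 also admits patients on a non-rebreather, high-flow cannula or non-invasive ventilation. It belongs in the range but does not remove the problem; at very high mortality the scoring of deaths dominates.

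Several stronger readings are tempting, and the documents do not support them:
- A reader might infer that the plan cuts stays at Day 28. It is silent; cutting and dropping are both open to the analyst.
- A reader might infer that nothing is recorded after Day 28. Attributed SAEs still are (5.3.1, 5.4.4.2), and nothing forbids noting a later discharge. What is missing is any scheduled collection of it.
- A reader might compute the loss among survivors only. With the same inputs the share on support is 0.35/0.50 = 0.70 v 0.20/0.70 = 0.286. The cut difference is 8 x 0.414 = 3.3 days, against (8 + X) x 0.414 = 7.5, 11.6 or 15.7 days in full. Section 2.3 keeps deaths in, so those ratios do not describe the planned analysis, and a general claim that the cut shrinks a real benefit is not established.
- A reader might treat the unstated time origin as a source of bias. Days before randomization are balanced in expectation and add noise.

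**Conclusion.** The point holds as a minor one: a cheap improvement. As written, the plan yields a mean that does not estimate length of stay, because survivors still admitted at Day 28 have no rule and deaths enter as short stays.

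The number of controls affected runs from at least 9 of 20 at 40% mortality to possibly none at 85% or more, if patients on respiratory support are inpatients. In the illustration, cutting at Day 28 removes 1.5 to 4.5 days from the arm difference. The cut difference lies between -1.8 and +0.2 days, so it can show a shorter stay in the arm with more deaths. These day counts rest on the assumed mortality, stay lengths and times of death; only the good-outcome rates come from the plan.

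**What to change.** In Sections 2.3 and 6.5, and to match in 1.5, replace mean hospital length of stay by time from randomization to discharge alive within 28 days. Treat death as a competing event and censor patients still admitted at Day 28. Give the Aalen-Johansen cumulative incidence by arm with Gray's test, and report the percentage discharged alive by Day 28 in each arm. State how transfer to another facility is counted.

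If a number of days is still wanted, report a labelled measure restricted to 28 days, such as hospital-free days to Day 28 with deaths set to 0. This would sit naturally beside the ICU-free days already listed.

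The cost is SAP wording and one standard analysis. The dates needed fall within the existing daily follow-up, and Section 4.5.6 already obtains the ordinal scale at Day 28 whether or not the patient has been discharged. No extra visits or patients are needed. The downside is that the familiar mean stay is no longer reported.

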4.5.5 Follow Up Period (Day 4 -27)

The subject will have a daily follow up collecting all of the below assessments. If the patient reaches an aPTT value of 70-90 seconds, subsequently daily aPTT values will be record until discharge or Day 28.

- Neurological Exam

- Vitals

- Laboratory Samples (Standard of care)

- Respiratory Status / Ventilator Settings

- Ordinal Scale Assessment

- Imaging (Standard of Care)

- Concomitant medication review (excluding “prn” or “as needed” medications)

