6.2 PRIMARY EFFICACY VARIABLE

Data will be analyzed according to clinical status at day 28. Outcome will be the proportion of patients who are alive and free of respiratory failure (no use of HFNC, NIPPV, Intubation). All other patients, those on HFNC, NIPPV, or mechanical ventilation, or dead, will be assessed as

Tenecteplase-Icahn School of Medicine at Mount Sinai
Protocol ML42492

37

failures for the purposes of the primary analysis. In the case of missing data, a last carry forward methodology will be used.

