- j. A woman is considered to be of childbearing potential if she is postmenarcheal, has not reached a postmenopausal state (\geq 12 continuous months of amenorrhea with no identified cause other than menopause), and has not undergone surgical sterilization (removal of ovaries and/or uterus). Urine/serum pregnancy test: all women of childbearing potential will have a pregnancy test at screening. If a urine pregnancy test is positive, it must be confirmed by a serum pregnancy test.
- k. All AEs that occur after signing the ICF and up to the EOS visit must be recorded. AESI's for this study protocol include: bleeding, hypersensitivity, thromboembolism, cholesterol embolization and arrhythmias. post-permanent SD discontinuation.
 - * To be performed q12h.
 - ** To be performed daily until a 2 point improvement in the ordinal scale assessment OR until 27 days OR until death OR discharge.
 - *** For patients already on heparin.

Tenecteplase—Icahn School of Medicine at Mount Sinai
Protocol ML42492

47

Effective Date: 6/15/2021

End Date: 12/7/2021

Appendix 2

Safety Reporting Fax Cover Sheet

A Member of the Roche Group

SAFETY REPORTING FAX COVER SHEET

GENENTECH SUPPORTED RESEARCH

AE / SAE [contact]

Genentech Study Number	
Principal Investigator	
Site Name	
Reporter name	
Reporter Telephone #	
Reporter Fax #	

Initial Report Date	[DD] / [MON] / [YY]
Follow-up Report Date	[DD] / [MON] / [YY]

Patient Initials (Enter a dash if patient has no middle name)	[] - [] - []
--	-----------------

SAE or Safety Reporting questions, contact Genentech Drug Safety: [contact]

PLEASE PLACE MEDWATCH REPORT or SAFETY REPORT BEHIND THIS COVER SHEET

Appendix 3

FDA MedWatch 3500 Form

This form is included in the study start-up zip file to be sent to sites via email.

Tenetecplase-Icahn School of Medicine at Mount Sinai
Protocol **ML42492**

49

Effective Date: 6/15/2021

End Date: 12/7/2021

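### Secondary outcomes are counted only until death, with no death value for length of stay or free days, and Appendix 1 conflicts with Sections 4.5.5 and 4.5.6 on when respiratory status and the final assessment stop

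*Combined protocol and SAP*

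**What the plan says.** **Deaths.** Section 2.3.C states that "patients who die will be included in statistical analysis" and then that "Variables of interest will be calculated until the point these patients expire". The outcomes listed just above it, in 2.3.B, include ventilator-, respiratory-failure-, vasopressor- and ICU-free days and hospital length of stay. They are named without a counting window or a value for death. Section 6.5 offers means with standard deviations, Tukey comparisons, logistic regression and Kaplan-Meier curves. It gives no death score, ranking or competing-event method. Section 6.2 scores death as failure, for the primary endpoint only.

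**Respiratory status, Days 4 to 27.** Section 4.5.5 says "The subject will have a daily follow up collecting all of the below assessments", and respiratory status is on its list. Appendix 1, footnote **, says of the same item: "To be performed daily until a 2 point improvement in the ordinal scale assessment OR until 27 days OR until death OR discharge".

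**Final assessment.** Section 4.5.6 says "The ordinal scale assessment will be completed at day 28 regardless of whether the patient is admitted or discharged". The last column of the Appendix 1 flowchart is headed "End of Study (Day 28 OR Discharge". Behind this stands Section 6.2: "In the case of missing data, a last carry forward methodology will be used".

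**The concern.** Section 2.3.C is a stated rule, so an analyst could follow it as written. A death on day 5 would then enter as a 5-day stay. A patient extubated on day 5 who dies on day 15 would keep 15 - 5 = 10 ventilator-free days. Length of stay can therefore favour the arm with more deaths, and free days can understate a survival benefit.

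Deaths will not be rare. Section 2.3.C itself expects high mortality, and Section 1.5 cites mortality of up to 88% in intubated patients. Section 3.3 says the trial is meant to estimate a benefit signal for a phase III trial, so distorted secondary estimates would feed into that design.

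The two schedule conflicts affect the data themselves. If respiratory status stops at improvement, an inpatient who goes back on support may have no record of it in the data used for free days. If the final visit is closed at discharge, the day-28 status needed for the primary may be missing and filled by carry-forward.

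**Working it through.** The documents give no length-of-stay or free-day figures, so there is no stated result to reproduce. The stays, death days and mortality rates below are assumptions.

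**1. Length of stay, 40% versus 60% mortality.** Let survivors stay S days and deaths occur on day D. Mean stay = (1 - mortality) × S + mortality × D. The difference between arms is 0.2 × (S - D), in favour of the deadlier arm.

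- S = 20, D = 5: 14.0 versus 11.0, difference 3.0 days.
- S = 20, D = 10: 16.0 versus 14.0, difference 2.0 days.
- S = 15, D = 10: 1.0 day. S = 25, D = 5: 4.0 days.

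**2. Length of stay at the planning rates.** Section 6.1 assumes "a good outcome rate of 15% in the control arm" and a 35-point improvement, so 15% versus 50%. Let successes stay S days, let a share d of failures die on day D, and let the remaining failures stay 28 days. Treated minus control = 0.35 × (S - d × D - (1 - d) × 28). A positive value means the better arm looks worse. The sign changes at d = (28 - S)/(28 - D).

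| S | d = 0.5, D = 10 | d = 1, D = 5 | Sign changes at d |
|---|---|---|---|
| 20 | 0.35 × (20 - 5 - 14) = 0.35 | 0.35 × (20 - 5) = 5.25 | 8/23 = 0.35 to 8/18 = 0.44 |
| 15 | 0.35 × (15 - 5 - 14) = -1.40 | 0.35 × (15 - 5) = 3.50 | 13/23 = 0.57 to 13/18 = 0.72 |

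With 20-day stays the better arm looks 0.4 to 5.3 days worse when 50% to 100% of failures are deaths. With 15-day stays the range runs from 1.4 days better to 3.5 days worse.

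**3. Free days, 40% versus 60% mortality.** Assume freedom from support starts uniformly between days 3 and 19 (mean 11), deaths are uniform between days 5 and 27, and the window is 28 days. Survivors average 28 - 11 = 17 free days. With death scored 0, the contrast is 0.2 × 17 = 3.4 days.

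Suppose those who die follow the survivors' schedule until death. Mean retained days are (t - 3)²/32 for death on day t up to 19, and t - 11 after that. Averaged over days 5 to 27 this is (42.58 + 96)/22 = 6.30 days, and (7.875 + 8)/22 = 72% come off support before dying. If only a fraction k of those who die follow that schedule, the contrast is 0.2 × (17 - 6.30k).

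| Share of deaths first off support | k | Contrast (days) | Loss |
|---|---|---|---|
| 72% | 1 | 2.1 | 37% |
| 36% | 0.5 | 2.8 | 19% |
| 18% | 0.25 | 3.1 | 9% |
| 0% | 0 | 3.4 | 0% |

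**4. Schedule conflicts.** No arithmetic applies.

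- Stopping respiratory status at death or discharge may be implicit in Section 4.5.5. Stopping at a 2-point improvement is not, so a site cannot follow both texts for an improved inpatient.
- The ordinal scale row carries no ** mark and stays daily, which covers part of the gap. Its categories are not defined in the documents, so whether it recovers the type of support cannot be judged.
- A site that closes follow-up at discharge has no day-28 ordinal score. Section 6.2 then carries forward the discharge status, which would normally count as success.

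**The case against.** The best counter-argument has four parts.

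- **The magnitudes rest on assumed inputs and do not fix a direction.** This stands. At the planning rates the sign changes with S and d, and the 28-day stay for surviving failures is itself an assumption, because the plan states no cap. With 35 days instead, S = 20, d = 0.5 and D = 10 give 0.35 × (20 - 5 - 17.5) = -0.9, so the better arm looks better. The free-day loss is at most 9% if no more than 18% of those who die had come off support, and no scenario here reverses the contrast. What remains is that the estimate depends on the mix of deaths and survivors, under a rule the plan states.
- **The harm from the death rule is to secondary outcomes only**, in a trial that Section 3.3 says is not powered for significance, with 28-day mortality reported separately. This also stands, and it limits the severity.
- **The flowchart heading is only a column label, and Section 4.5.6 is explicit.** Death by day 28 should reach the primary anyway, because mortality is tracked and deaths in follow-up trigger committee review under Section 5.1.1. The exposure is then mainly a patient discharged off support, readmitted, and on support at day 28. The documents do not say how often that would happen. The conflict is narrow, but it can reach the primary.
- **The respiratory-status gap is partly covered** by the daily ordinal scale, and day-28 respiratory status is still collected for inpatients. This reduces the gap but does not reconcile the two texts.

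**Conclusion.** The concern holds. As written, Section 2.3.C counts length of stay and free days only until death, and no other section supplies a death value. Under 40% versus 60% mortality and 20-day survivor stays, the deadlier arm looks 2.0 to 3.0 days better on length of stay (1.0 to 4.0 days for stays of 15 to 25 days). At the Section 6.1 rates the distortion can reach 5.3 days, but its sign is uncertain. Free-day contrasts lose 0% to about 37%, depending on how many of those who die were first off support. All these sizes are illustrations on assumed stays, death days and mortality.

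The primary is not affected by the death rule. It can be affected by the final-visit conflict, through carry-forward, to an extent the documents do not allow to be estimated. This should be corrected before analysis: in a trial of 60 patients, a death score chosen after seeing the data would be open to challenge.

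**What to change.** - **Section 2.3.C:** state the counting window for each free-day outcome, to day 28, and score all of them 0 for death by day 28. Analyse length of stay as time to discharge alive with death as a competing event, or rank deaths worst. Add the matching method to Section 6.5.
- **Appendix 1, footnote **:** delete the stop at a 2-point improvement, so that it matches Section 4.5.5.
- **Appendix 1, last column:** reword the heading so that the final ordinal assessment is at day 28 for everyone, as Section 4.5.6 requires. Carry-forward should then rarely be needed for the primary.
- **Section 6.2:** add a sensitivity analysis that counts unknown day-28 status as failure. It is one bound, and could penalise an arm with more early discharges, so report it beside the carry-forward result.

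The cost is wording in 2.3.C and 6.5, one deleted clause, one corrected heading and one sensitivity analysis. The daily respiratory entries and day-28 contacts are already required by Sections 4.5.5 and 4.5.6.
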